#### 10.2.10 Interim Analysis

No interim analysis is planned for this study.

#### 11 STUDY GOVERNANCE CONSIDERATIONS

#### 11.1 Quality Control

In accordance with applicable regulations including GCP, and GSK procedures, GSK or designee (i.e. third party vendor) monitors will contact the site prior to the start of the study to review with the site staff the protocol, study requirements, and their responsibilities to satisfy regulatory, ethical, and GSK requirements.

When reviewing data collection procedures, the discussion will include identification, agreement and documentation of data items for which the CRF will serve as the source document.

GSK or designee will monitor the study and site activity to verify that the:

- Data are authentic, accurate, and complete.
- Safety and rights of subjects are being protected.
- Study is conducted in accordance with the currently approved protocol and any other study agreements, GCP, and all applicable regulatory requirements.

The extent and nature of monitoring will be described in a written monitoring plan on file at GSK CH. The investigator (or designee) agrees to allow the monitor direct access to all relevant documents and agrees to co-operate with the monitor to ensure that any problems detected in the course of these monitoring visits are resolved.

#### 11.2 Quality Assurance

To ensure compliance with GCP and all applicable regulatory requirements, GSK may conduct a quality assurance assessment and/or audit of the site records, and the regulatory agencies may conduct a regulatory inspection at any time during or after completion of the study.

In the event of an assessment, audit or inspection, the investigator (and institution) must agree to grant the advisor(s), auditor(s) and inspector(s) direct access to all relevant documents and to allocate their time and the time of their staff to discuss the conduct of the study, any findings/relevant issues and to implement any corrective and/or preventative actions to address any findings/issues identified.

The investigator(s) will notify GSK CH or its agents immediately of any regulatory inspection notification in relation to the study. Furthermore, the investigator will cooperate with GSK CH or its agents to prepare the study site for the inspection and will allow GSK CH or its agent, whenever feasible, to be present during the inspection. The investigator will promptly apply copies of the inspection finding to GSK CH or its agent. Before response submission to the

GlaxoSmithKline Consumer Healthcare Confidential Template Version Effective: 22-Jun-2017 Page **63** of **71**  regulatory authority, the investigator will provide GSK CH or its agents with an opportunity to review and comment on responses to any such findings.

The sponsor will be available to help investigators prepare for an inspection.

#### 11.3 Regulatory and Ethical Considerations

#### 11.3.1 Institutional Review Board/ Ethics Committee

It is the responsibility of the investigator to have prospective approval of the study protocol, protocol amendments, informed consent documents, investigator brochure/safety statement (including any updates) and other relevant documents, e.g., recruitment advertisements, if applicable, from the IRB/EC. All correspondence with the IRB/EC should be retained in the investigator file. Copies of IRB/EC approvals should be forwarded to GSK CH prior to the initiation of the study, and also when subsequent amendments to the protocol are made.

The only circumstance in which an amendment may be initiated prior to IRB/EC approval is where the change is necessary to eliminate apparent immediate hazards to the subjects. In that event, the investigator must notify the IRB/EC and GSK CH in writing immediately after the implementation.

#### 11.3.2 Ethical Conduct of the Study

The study will be conducted in accordance with legal and regulatory requirements, as well as the general principles set forth in the International Ethical Guidelines for Biomedical Research Involving Human Subjects (Council for International Organizations of Medical Sciences 2002), guidelines for GCP (ICH 1996 and revision 2), and the Declaration of Helsinki (World Medical Association 2013).

In addition, the study will be conducted in accordance with the protocol, the ICH guideline on GCP, and applicable local regulatory requirements and laws.

#### 11.3.3 Subject Information and Consent

All parties will ensure protection of subject personal data and will not include subject names or other identifiable data in any reports, publications, or other disclosures, except where required by laws.

When study data are compiled for transfer to GSK CH and other authorized parties, subject names, addresses, and other identifiable data will be replaced by numerical codes based on a numbering system provided by GSK CH in order to de-identify study subjects.

The study site will maintain a confidential list of subjects who participated in the study, linking each subject's numerical code to his or her actual identity. In case of data transfer, GSK CH will maintain high standards of confidentiality and protection of subjects' personal data consistent with applicable privacy laws.

The informed consent documents must be in compliance with ICH GCP, local regulatory requirements, and legal requirements, including applicable privacy laws.

GlaxoSmithKline Consumer Healthcare Confidential Template Version Effective: 22-Jun-2017 The informed consent documents used during the informed consent process must be reviewed and approved by the sponsor, approved by the IRB/EC before use, and available for inspection.

The investigator must ensure that each study subject, is fully informed about the nature and objectives of the study and possible risks associated with participation.

The investigator, or a person designated by the investigator, will obtain written informed consent from each subject before any study-specific activity is performed. The investigator will retain the original of each subject's signed informed consent document.

#### 11.3.4 Subject Recruitment

Advertisements approved by IRBs/ECs and investigator databases may be used as recruitment procedures. Use of ethics committee approved, generic, prescreening questionnaire to assess basic subject characteristics to determine general eligibility for this study is allowed. This generic questionnaire may be used by sites as a phone script and/or to review internal databases to identify subjects.

GSK CH will have an opportunity to review and approve the content of any study recruitment materials directed to potential study subjects before such materials are used.

## 11.3.5 Reporting of Safety Issues and Serious Breaches of the Protocol or ICH GCP

Within GSK CH a serious breach is defined as a breach likely to affect to a significant degree the safety and rights of a subject or the reliability and robustness of the data generated in GSK CH- sponsored human subject research studies.

In the event of any prohibition or restriction imposed (i.e., clinical hold) by an applicable competent authority in any area of the world, or if the investigator is aware of any new information that might influence the evaluation of the benefits and risks of the investigational product, GSK CH should be informed immediately.

In addition, the investigator will inform GSK CH immediately of any urgent safety measures taken by the investigator to protect the study subjects against any immediate hazard, and of any serious breaches of this protocol or of ICH GCP that the investigator becomes aware of.

# 11.4 Posting of Information on Publicly Available Clinical Trial Registers

Study information from this protocol will be posted on publicly available clinical trial registers before enrollment of subjects begins in accordance with applicable GSK processes.

## 11.5 Provision of Study Results to Investigators

Where required by applicable regulatory requirements, an investigator signatory will be identified for the approval of the clinical study report. The investigator will be provided

GlaxoSmithKline Consumer Healthcare Confidential Template Version Effective: 22-Jun-2017 Page **65** of **71**  reasonable access to statistical tables, figures, and relevant reports and will have the opportunity to review the complete study results at a GSK site or other mutually-agreeable location.

GSK will also provide the investigator with the full summary of the study results. The investigator is encouraged to share the summary results with the study subjects, as appropriate.

The procedures and timing for public disclosure of the results summary and for development of a manuscript for publication will be in accordance with GSK Policy.

A manuscript will be progressed for publication in the scientific literature if the results provide important scientific or medical knowledge.

#### 11.6 Records Retention

Following closure of the study, the investigator must maintain all site study records (except for those required by local regulations to be maintained elsewhere), in a safe and secure location.

The records (study/ site master file) must be maintained to allow easy and timely retrieval, when needed (e.g., for a GSK audit or regulatory inspection) and must be available for review in conjunction with assessment of the facility, supporting systems, and relevant site staff.

Where permitted by local laws/regulations or institutional policy, some or all of these records can be maintained in a format other than hard copy (e.g., microfiche, scanned, electronic); however, caution needs to be exercised before such action is taken.

The investigator must ensure that all reproductions are legible and are a true and accurate copy of the original and meet accessibility and retrieval standards, including re-generating a hard copy, if required. Furthermore, the investigator must ensure there is an acceptable back-up of these reproductions and that an acceptable quality control process exists for making these reproductions.

The investigator must assure that the subject's anonymity will be maintained. On CRFs or other documents submitted to GSK CH, subjects should not be identified by their names or initials, but by an identification code. The investigator should keep a separate log of subjects' codes, names and addresses. Documents not for submission to GSK CH, e.g. subjects' written consent forms, should be maintained by the investigator in strict confidence.

Records and documents, including signed ICF, pertaining to the conduct of this study must be retained by the investigator for 25 years from the issue of the final Clinical Study Report (CSR)/ equivalent summary unless local regulations or institutional policies require a longer retention period. The minimum retention time will meet the strictest standard applicable to that site for the study, as dictated by any institutional requirements or local laws or regulations, GSK standards/procedures, and/or institutional requirements.

No study document should be destroyed without a prior written agreement between GSK CH and the investigator. The investigator must notify GSK of any changes in the archival arrangements, including, but not limited to, archival at an off-site facility or transfer of ownership of the records in the event the investigator is no longer associated with the site.

## 11.7 Conditions for Terminating the Study

Premature termination of this study may occur because of a regulatory authority decision, change in opinion of the IRB/EC, or investigational product safety problems, or at the discretion of GSK CH. For multicenter studies (if applicable), this can occur at one or more or at all sites.

If a study is prematurely terminated, GSK CH will promptly notify the investigator. After notification, the investigator must promptly contact all participating subjects and should assure appropriate therapy/ follow-up for the subjects. As directed by GSK CH, all study materials must be collected and all CRFs completed to the greatest extent possible. Where required by the applicable regulatory requirements, GSK CH should inform the regulatory authority(ies) and the investigator should promptly inform the IRB/EC and provide the IRB/EC a detailed written explanation of the termination or suspension.

If the IRB/EC terminates or suspends its approval/favorable opinion of a trial, the investigator should promptly notify the GSK CH and provide GSK CH with a detailed written explanation of the termination or suspension.

Upon completion or premature discontinuation of the study, the GSK CH monitor will conduct site closure activities with the investigator or site staff, as appropriate, in accordance with applicable regulations including GCP, and GSK CH Standard Operating Procedures.

#### 11.8 Definition of Study End/ End of Study

The study end date will be the same date as Last Subject Last Visit.

#### 13 APPENDIX

#### 13.1 ABBREVIATION

The following is a list of abbreviations that may be used in the protocol.

Table 13-1 Abbreviation

Abbreviation	Term
AE	adverse event
ALT	alanine transaminase
AST	aspartate transaminase
b.i.d.	twice daily
BLOQ	below the limit of quantification
BMI	body mass index
BP	blood pressure
BUN	blood urea nitrogen
CO 2	carbon dioxide (bicarbonate)
COX-2	cyclo-oxygenase 2
CRF	case report form
DDEA	Diclofenac diethylamine
EC	ethics committee
ECG	electrocardiogram
EDTA	edetic acid (ethylenediaminetetraacetic acid)
EudraCT	European Clinical Trials Database
FSH	follicle-stimulating hormone
GCP	Good Clinical Practice
GGT	gamma-glutamyl transpeptidase
hCG	human chorionic gonadotropin
HIV	human immunodeficiency virus
IB	investigator's brochure
ICH	International Conference on Harmonisation
INR	international normalized ratio
IRB	institutional review board
	intrauterine device

GlaxoSmithKline Consumer Healthcare Confidential Template Version Effective: 22-Jun-2017

Abbreviation	Term
K2-EDTA	potassium-ethylenediaminetetraacetic acid
LOQ	Limit Of Quantification
max	maximum
MCH	Mean corpuscular hemoglobin
MCHC	Mean corpuscular hemoglobin concentration
MCV	Mean corpuscular volume
MedDRA	medical Dictionary for Regulatory Activities
min	minimum
N/A	not applicable
NICE	National Institute for Health and Care Excellence
NSAID	non-steroidal anti-inflammatory drug
OA	osteoarthritis
OTC	over-the-counter
P10	10 th percentile
P90	90 th percentile
PD	pharmacodynamics
PG	prostaglandin
PGE 2	prostaglandin E2
PI	principal investigator
PK	pharmacokinetics
PP	Per-Protocol
PR	pulse rate
PT	prothrombin time
Q1	First quartile
Q3	Third quartile
RAP	reporting analysis plan
RBC	red blood cell
RR	respiratory rate
SAE	serious adverse event
SCr	serum creatinine
SD	standard deviation
SOC	System Organ Class
SRSD	single reference study document
SS	safety statement
SUSAR	suspected unexpected serious adverse reaction
T 1/2	terminal half-life
TEAE	Treatment Emergent adverse event
TKR	total knee replacement
US	United States

GlaxoSmithKline Consumer Healthcare Confidential Template Version Effective: 22-Jun-2017

Page **70** of **71** 

Diclofenac Diethylamine 2.32% 208901

Final Clinical Protocol 12 Feb 2018

Abbreviation	Term
WBC	white blood cell

### **Document History**

Document	Version Date	Summary of Changes (New analysis or Change in planned analysis)
Original Analysis Plan	08 May 2019	Not applicable (N/A)

## List of Abbreviations

Abbreviation	Description
AE	Adverse Event
ATC	Anatomical Therapeutic Chemical
b.i.d.	Twice Daily
BDRM	Blind Data Review Meeting
BMI	Body Mass Index
COX-2	Cyclo-oxygenase 2
CRF	Case Report Form
DDEA	Diclofenac Diethylamine
ECG	Electrocardiogram
GSKDRUG	GSK Drug Coding Dictionary
LOQ	Limit of Quantification
MedDRA	Medical Dictionary for Regulatory Activities
N/A	Not Applicable
OA	Osteoarthritis
РР	Per Protocol
PP-PD	Per Protocol Pharmacodynamic
SOC	System Organ Class
TEAE	Treatment Emergent Adverse Event

The purpose of this Statistical Reporting and Analysis Plan is to describe the planned analyses and outputs to be included in the Clinical Study Report for Protocol 208901.

## 1 Summary of Key Protocol Information

The purpose of this study is to evaluate the exposure of diclofenac in the plasma and in the knee joint following topical administration of 2.32% diclofenac diethylamine (DDEA) gel (Voltarol 12 Hour Emulgel P 2.32% Gel in the UK, Voltaren Schmerzgel forte 23.2 mg/g gel in Germany) 4 g applied twice daily (b.i.d.) for 7 days.

This will be a randomized, double-blind, multi-center, placebo-controlled clinical study investigating the concentration of topically applied diclofenac achieved in the knee joint synovial tissue and synovial fluid following b.i.d dosing for seven days.

The study will be performed in subjects diagnosed with osteoarthritis (OA) of the knee who are scheduled for arthroplasty of the knee as a treatment for their OA.

### 1.1 Study Design

Approximately fifty (50) male and female OA subjects, who, at the time of screening, are  $\geq$ 50 years old, will be randomized in a 2:1 ratio: two thirds will receive DDEA 2.32% gel treatment and one third placebo gel.

After providing informed consent to participate in the study the subjects will need to forego any NSAID or cyclo-oxygenase 2 (COX-2) treatment for at least 7 days prior to starting study treatment (Visit 2) in order to allow wash-out of existing therapy and thus avoiding confounding the effect of the study treatments. Dosing will be scheduled to commence seven days prior (at minimum) to the scheduled surgery and will occur twice a day following dosing instructions. If surgery is delayed dosing with study treatment can continue up to 14 days.

A schematic of the study design is provided in Figure 1-1.

#### Figure 1-1 A schematic of the study design

### 1.2 Study Objectives

Objectives	Endpoints	
Primary Objective	Primary Endpoint	
• To determine whether diclofenac penetrates into treated knee joint following repeated topical administration of diclofenac diethylamine 2.32% gel.	
 
Diclofenac concentration in treated knee synovial tissue and synovial fluid after 7 days topical application of study treatment to the knee (12 hours after last application)
 
	
Secondary Objectives	Secondary Endpoints	

 
To evaluate the relative exposure of diclofenac in the knee joint vs. plasma.
 
	
 
Ratio between diclofenac concentration in treated knee synovial tissue and diclofenac plasma concentration (sample taken during surgery) after 7 days topical application of study treatment to the knee (12 hours after last application)
 
	
	
 
Ratio between diclofenac concentration in treated knee synovial fluid and diclofenac plasma concentration (sample taken during surgery) after 7 days topical application of
 
	

Objectives	Endpoints	
	study treatment to the knee (12 hours after last application)	
Exploratory Objectives	Exploratory Endpoints	

 
To evaluate treatment effects upon COX- 2 inhibition in the knee joint
 
	
 
PGE2 levels in treated knee synovial tissue and synovial fluid after 7 days topical application of study treatment to the knee (12 hours after last application)
 
	
To evaluate treatment effects upon inflammatory cytokines in the knee joint	
 
IL-6 and TNFα levels in treated knee synovial tissue and synovial fluid after 7 days topical application of study treatment to the knee (12 hours after last application)
 
	

### 1.3 Treatments

The study includes one active treatment arm and one placebo control arm.

In the treatment arm, DDEA 2.32% gel will be applied to the knee planned for arthroplasty surgery (target knee). If the subject has bilateral knee OA, the treatment will be applied to the knee planned for surgery only and not to the contralateral knee. A placebo control arm is included to facilitate bioactivity comparisons. In the placebo control arm a placebo gel will be applied in a similar manner as the DDEA 2.32% gel on the knee planned for surgery (target knee).

### 1.4 Sample Size Calculation

A formal estimation of sample size was not carried out. The sample size selected (approximately 30 subjects on active, 15 subjects on placebo control) for the present study is in general agreement with similar studies (Benito 2005, Gallelli 2013, Gallelli 2012, Alvarez-Soria 2006, Fowler 1983, Efe 2014) and is deemed adequate to provide information on diclofenac concentration(s) in treated knee synovial tissue and synovial fluid.

Approximately 50 subjects will be randomized to account for 10% dropout and ensure evaluable data for 45 subjects who underwent the surgery.

## 2 Planned Analyses

### 2.1 Interim Analysis

No interim analysis is planned.

### 2.2 Final Analyses

The final planned primary analyses will be performed after the completion of the following sequential steps:

GlaxoSmithKline Consumer Healthcare Confidential Page 9 of 22

- 1. All subjects have completed the study as defined in the protocol.
- 2. All required database cleaning activities have been completed and database has been locked.

### 3 Considerations for Data Analyses and Data Handling Conventions

### 3.1 Baseline Definition

For all endpoints, the baseline value is the latest pre-dose assessment with a non-missing value.

### 3.2 Centers Pools

This study is a multicenter study. Data will be summarized for all centers combined. Statistical analyses will not be adjusted for centers.

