# 5.1 Blinding and Allocation to Treatment/Randomization

At Visit 2, participants who fulfill all the inclusion criteria and none of the exclusion criteria will be assigned a unique randomization number in ascending numerical order at each study site. The randomization number encodes the participant's assignment to one of the two arms of the study according to the randomization schedule generated prior to the study by the Statistics Department at PPD. These randomization numbers are linked to the two treatment arms, which in turn are linked to container (kit) numbers. A separate container list will be produced by the Statistics Department at PPD. Subjects will be randomized using an interactive response technology system and container numbers will be provided by the system.

Subjects will be randomized in a 2:1 ratio: approximately two thirds will receive DDEA 2.32% gel treatment and one third placebo gel. Consecutive blocks of randomization numbers will be assigned to individual centers in order to stratify the randomization by center.

This is a double-blind study. The subjects, investigators and site staff, study statistician and other employees of the sponsor and vendors acting on behalf of the sponsor who may influence study outcomes will be blinded to the treatment allocation of subjects. The placebo gel and the active gel will be identical in packaging, labeling, odor, schedule of administration, and as identical as possible in appearance.

Randomization data will be kept strictly confidential by PPD, accessible only to authorized persons, until the time of unblinding. After the study is completed, the data file verified, and protocol violations determined, drug codes will be broken and made available for data analysis.

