#### 6.2.3 Pre-Surgery Day 7 and Surgery Day 8 (Visit 3)

The subject will be admitted to the study site in the afternoon of Day 7 and remain at the study site until discharge post-surgery. The surgery will take place in the morning of Day 8, 12 hours (window -1/+3 hrs) after last dose of study treatment.

The surgery may be delayed by up to 7 days, in which case the study treatment will continue to be applied twice daily up to 14 days. If the surgery is delayed by more than 7 days, the subject should be withdrawn from the study. Subject Withdrawal/Early Termination assessments will be conducted (See Section 6.4 Subject Withdrawal). No further PK blood samples will be collected and the rescheduled surgery will not be part of the study.

On Day 7 (pre-surgery), the following procedures will be completed and results recorded in source documents:

- Collect all returned study treatment
- Collect all returned rescue medication
- Review concomitant medications
- Review any AEs (continuing up to surgery)
- Collect a blood sample for pharmacokinetic analysis within 1 hour prior to last dosing.
- Dose subject with final dose of study treatment (12 hours (window -1/+3 hrs) prior to surgery)

**After dosing**, (ie. Between final dosing with study treatment and prior to surgery) the following procedures will be completed:

- Conduct physical examination and collect vital signs (BP, PR, RR, temperature)
- Collect standard 12-lead ECG measurements
- Following at least a 4 hour fast, collect blood and urine specimens for safety laboratory tests
- Collect one blood sample for diclofenac levels —at least 3 hours after dosing and more than 3 hours before surgery
- The subject will be prepared for surgery according to the procedures of the surgical center; if shaving of the knee area is required, this should occur as close as possible to the surgery but in any event no less than 3 hours after dosing

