#### **During Surgery**

- The surgery will be conducted according to the surgical procedures of the surgical center
- One final blood sample for PK analysis will be collected (between anaesthesia and completion of surgery)
- Four (4) aliquots of 2.5-3 mL of synovial fluid will be collected as described in the Laboratory Study Manual

GlaxoSmithKline Consumer Healthcare Confidential Template Version Effective: 22-Jun-2017 • Two (2) synovial tissue samples of approximately 2 to 3 cm^3 each will be collected as described in the Laboratory Study Manual

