### 4.6.1 Exploratory Endpoints

The exploratory endpoints are

GlaxoSmithKline Consumer Healthcare Confidential Page 17 of 22

- PGE2 levels in treated knee synovial tissue and synovial fluid after 7 days topical administration to the knee (12 hours after last application)
- IL-6 and TNF $\alpha$  levels in treated knee synovial tissue and synovial fluid after 7 days topical administration to the knee (12 hours after last application)

The success criteria for exploratory objectives are

- diclofenac reduces PGE2 levels in treated knee synovial tissue or synovial fluid after 7 days topical administration to the knee compared to placebo gel
- diclofenac reduces levels of inflammatory cytokines i.e. TNFα and/or IL-6 associated with OA in treated knee synovial tissue or synovial fluid after 7 days topical administration to the knee compared to placebo gel

 $PGE_2$  and inflammatory cytokines levels will be summarized descriptively in both the arithmetic and the logarithmic scale (Table 14.2.6 - Table 14.2.11). The mean, SD, min, P10, Q1, median, Q3, P90 and max will be summarized.

For each endpoint, the success criterion will be addressed by a two-sided test for superiority at level alpha=0.05 in an exploratory manner. Log-transformed mean levels will be compared between treatment groups using an analysis of variance including treatment as a fixed effect. The two-sided 95% confidence interval for the ratio of geometric means on the original scale will be derived by back-transforming the confidence interval for the difference between treatment groups on the log-transformed scale obtained from the analysis.

The analyses will be performed on the analysable population.

The analyses will be repeated for the PP-PD (Per Protocol Pharmacodynamic) Population (Table 14.2.13 - Table 14.2.18).

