## 5 Changes to the Protocol Defined Statistical Analysis Plan

Any changes from the originally planned statistical analysis specified in the protocol are outlined in Table 5-1.

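### Randomization is stratified by center, but the exploratory biomarker ANOVA leaves center out without a reason; if centers differ, its intervals are wider than they need to be

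*SAP*

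**What the plan says.** Protocol 5.1 sets up the allocation: "Consecutive blocks of randomization numbers will be assigned to individual centers in order to stratify the randomization by center". The ratio is 2:1; the block size and the number of centers are not stated.

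SAP 3.2 combines all centers and adds: "Statistical analyses will not be adjusted for centers". It gives no reason.

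The only between-arm tests in the plan concern PGE2, IL-6 and TNFα in synovial tissue and fluid, six endpoints in all. SAP 4.6.1 specifies: "Log-transformed mean levels will be compared between treatment groups using an analysis of variance including treatment as a fixed effect". Each test is two-sided at 0.05 and labelled exploratory. Protocol 10.2.8 has the same model, so protocol and SAP agree with each other.

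SAP 5 says "Any changes from the originally planned statistical analysis specified in the protocol are outlined in Table 5-1". Because the model did not change, that table has no entry on center. The reason is therefore missing from the plan as a whole, and Table 5-1 is not itself at fault.

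The purpose of the control group is stated in SAP 1.3: "A placebo control arm is included to facilitate bioactivity comparisons".

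**The concern.** When allocation is balanced within centers, a difference in level between centers largely cancels out of the treatment contrast. To benefit from that, the analysis must also take the center differences out of the residual variance. A treatment-only ANOVA does not. Its standard error still includes variation that the design has already removed from the estimate, so the interval over-covers and the test rejects too seldom.

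This matters only if biomarker levels differ between centers. Two provisions make that possible. Protocol 6.2.3 says of the pre-operative phase "The subject will be prepared for surgery according to the procedures of the surgical center", and of the operation itself "The surgery will be conducted according to the surgical procedures of the surgical center". Other provisions limit it: clean, previously unused sampling equipment (Protocol 3), nurse-applied doses by an established method (5.3, 5.5), a common laboratory manual (7.2.2), and biomarker analysis under one laboratory's responsibility (7.3).

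What is at stake is precision in the bioactivity comparison, where the smaller arm has about 15 evaluable subjects. The primary and secondary analyses are descriptive and are not touched.

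**Working it through.** **The plan's own figure.** SAP 1.4: "Approximately 50 subjects will be randomized to account for 10% dropout and ensure evaluable data for 45 subjects who underwent the surgery". 45 / (1 − 0.10) = 50, which reproduces. The evaluable split is about 30 active and 15 placebo. The plan states no power, SD, effect size or interval width for the biomarker ANOVA, so nothing else can be reproduced.

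**Assumed inputs.** The documents do not give the number of centers, block size, share ρ of log-scale variance lying between centers, or effect size. Ranges are used for the first three and a true difference of 0.9 total SD for power.

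**Step 1: formula for the ideal case.** Set total SD = 1, N = 45, k equal centers, exact 2:1 in each.

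- Contrast factor: √(1/30 + 1/15) = √0.1 = 0.316.
- Planned model, residual mean square: [(N−1−k)(1−ρ) + (k−1){(1−ρ) + (N/k)ρ}] / (N−2), with 43 df.
- Adjusted model, residual variance: 1−ρ, with 44−k df.

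For k = 5 and ρ = 0.2:

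- Planned: [39 × 0.8 + 4 × (0.8 + 9 × 0.2)] / 43 = 41.6 / 43 = 0.967. Half-width = 2.017 × √0.967 × 0.316 = 0.627.
- Adjusted: half-width = 2.023 × √0.8 × 0.316 = 0.572.
- Ratio 1.096: the planned interval is about 10% wider.

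The true standard error of the contrast is then √(0.8 × 0.1) = 0.283, while the planned model estimates √(0.967 × 0.1) = 0.311. That gap is the source of the over-coverage. Simulating this ideal case gave coverage of 97.1% planned and 95.4% adjusted, and rejection under no effect of 2.9% and 4.6%. Power at 0.9 SD was about 83% and 88%.

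For k = 5 and ρ = 0 the half-widths are 0.638 planned and 0.640 adjusted.

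**Step 2: simulation with dropout.** The formula favors adjustment, because losses and incomplete blocks disturb the 2:1 balance within centers. So 50 subjects were randomized 2:1 in permuted blocks of 3 or 6 within center, 5 were removed at random, and small centers were pooled by the rule given under the fix (10,000 trials per setting). Center sizes were 17/17/16, 13/13/12/12, five of 10, 24/10/9/4/3, ten of 5, and 14/9/7/5/4/3/3/2/2/1.

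| Center share ρ | Planned CI vs adjusted, 3–5 centers | Power change from adjusting, 3–5 centers | 10 centers, pooled |
|---|---|---|---|
| 0 | 0.5–1.5% narrower | −0.3 to −1.2 points | adjusted CI 2.2–3.3% wider |
| 0.05 | 0.3–1.3% wider | not tabulated | adjusted CI 0.1–1.2% wider |
| 0.1 | 2.1–3.5% wider | +0.9 to +1.9 | planned CI 0.9–1.9% wider |
| 0.2 | 6.5–8.6% wider | +3.6 to +4.5 | planned CI 5.4–7.1% wider |
| 0.3 | 11.4–14.5% wider | +5.1 to +6.9 | not tabulated |

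With 3 to 5 centers, coverage of the planned interval is about 96.1–96.6% at ρ = 0.2 and 96.2–97.2% at ρ = 0.3.

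Example, five centers of 10, blocks of 3: the planned/adjusted width ratio is 0.988, 1.009, 1.033, 1.086 and 1.145 at the five shares. A repeat with 3,000 trials per setting gave 0.989, 1.011, 1.031, 1.086 and 1.144.

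**Step 3: fewer evaluable samples.** The analysable population needs evaluable tissue or fluid, not both (Protocol 10.2.1), so a single endpoint can have fewer than 45 values. With 15 of 50 lost and 3 to 5 equal centers (5,000 trials per setting), the ratio is 0.972–0.987 at ρ = 0, meaning adjustment costs 1.3–2.9% in width, and 1.015–1.025 at ρ = 0.1.

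**The case against.** The strongest reply is that nothing in the plan is invalid. The choice is explicit, pre-specified and the same in both documents. The treatment-only intervals are valid, and conservative if centers differ. The endpoints are exploratory, and study success depends only on detecting diclofenac. All of this stands, and it limits the weight of the point.

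Second, the sign of the benefit cannot be settled from the documents. Sampling, handling, dosing and laboratory work are standardized, and no passage links local surgical practice to biomarker levels. With ten unequal centers at ρ = 0.1, a 3,000-trial run gave power of 79.8% planned and 80.5% adjusted, which is within simulation error. Gains of about 4 points need ρ near 0.2. This also stands, and it is why the result is given as a range that includes a loss.

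Third, pooling complicates the remedy. Strata may differ between endpoints and need not match the randomization strata. Pooling was triggered in 98% of simulated trials with ten unequal centers and in about a third with ten equal ones. That is a real cost, but a fixed rule keeps it free of post hoc choice, and the 10-center figures above already include it.

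Fourth, the plan sets no precision target against which an interval could be called too wide. A target is not needed to see the loss: if centers differ, the planned 95% interval covers more than 95% of the time, and the adjusted model gives a shorter interval from the same data.

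**Conclusion.** The concern holds. The plan stratifies by center, omits center from its only between-arm model, and does not say why. If centers differ, the cost is precision and power in the exploratory biomarker comparison. There is no bias, no false-positive inflation and no effect on the primary or secondary summaries.

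The size is conditional on assumed values. With 3 to 5 centers, adjustment pays from a center share somewhere below 0.05 and loses little if there is no center effect. With 10 centers, break-even lies between 0.05 and 0.1, and the possible loss is a few percent of interval width. The potential gain is larger than the potential loss, and the comparison is the stated purpose of the placebo arm. The change should therefore be made, but it is a moderate improvement to a plan that would otherwise still give valid tests.

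**What to change.** Before unblinding, amend SAP 3.2 and 4.6.1 along these lines:

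> The ANOVA of log-transformed PGE2, IL-6 and TNFα will include treatment and center as fixed effects. For each endpoint, centers without at least one evaluable subject in each arm are pooled into one stratum. If that stratum still lacks an arm, it is merged with the smallest remaining center (lowest center number if tied).

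Apply this to Tables 14.2.6–14.2.11 and, for the PP-PD population, 14.2.13–14.2.18. Keep the treatment-only model as a sensitivity analysis and add a row to Table 5-1. If the sponsor has a reason to leave center out, such as many very small sites, the minimum is to state it and pre-specify the adjusted model as the sensitivity analysis.

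The cost is a short text change, one model term with its pooling step, and one table row. The statistical price if centers do not differ is the loss shown at ρ = 0 in the working.
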